University of Maryland, Baltimore research staff virtually enroll participants and collect survey data from ACTs Continuing Care Retirement Communities where participants are living. ACTs Continuing Care Retirement Communities is a national organization that provides Medicare Part A skilled nursing benefit services and 11 communities are involved in the study. We plan to enroll patients throughout facilities located in Delaware, Maryland, New Jersey and/or Southeast Pennsylvania.
The PI will conduct data analysis at University of Maryland (UMB).
- 3 * Describe the availability of medical and/or psychological resources that subjects might need as a result of anticipated consequences of the human research:
Participants are residents of a skilled nursing facility and have 24 hour access to nursing and healthcare resources. The risks to participants are minimal because the study focuses on evidence-based assessment and management tools. Much of the data collected for the study is information that is similar (although more detailed) to that which is already captured for standard of care clinical purposes. Patients who are able to self-report will be queried regarding their pain, function, and mood, but again, this information is not outside the realm of what is collected for clinical purposes.
- 4 * Describe the process to ensure that all persons assisting with the research are adequately informed about the protocol, the research procedures, and their duties and functions:
The PI oversees recruitment, enrollment, data collection, and alerts/adverse events. A NIH approved DSMP is in place.
All study staff are trained on the protocol and standard operating procedures and duties.
All study staff will complete the NIH required training in the participation and conduct of studies that involve human subjects.

ID: VIEW4DF83CB976400
Name: v2_Resources

Sites Where Research Activities Will Be Conducted

1 * Is this study a:

Multi-Site
 Single Site

2 * Are you relying on an external IRB (not UM) to be the IRB of Record for this study?

Yes No

3 * Are any other institutions/organizations relying on UM to be the IRB of Record for this study?

Yes No

3.1

Attach the applicable regulatory documents here (i.e., IRB Authorization Agreement (IAA), FWA, local ethics approval, other IRB approvals, etc.). Final UM approval will be contingent upon final execution of all required regulatory approvals:

Name	Created	Modified Date
------	---------	---------------

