Page 10 of 18Satisfaction Questionnaire (CSQ). The CSQ is an 18 item patient/caregiver-report instrument that measures communication and satisfaction of a consult in four domains 1) general satisfaction, 2) professional care, 3) depth of relationship, 4) perceived length of consultation (scale format: 5-point Likert, strongly agree to strongly disagree). Source: patient or family caregiver; Time to complete: 3-5 minutes 2) Adherence to SNF-PCC recommendations: within 15 days post-SNF-PCC; measured by: medical record review.

2 * Discuss the research design including but not limited to such issues as: probability of group assignment, potential for subject to be randomized to placebo group, use of control subjects, etc.:

Pilot clinical trial with usual care control; 40 participants in each arm.

Aim 1 of this study is to establish the feasibility and acceptability of the SNF-PCC intervention.

Aim 2 of this study is to estimate the effect size of the SNF-PCC on the Palliative Outcomes Scale.

Aim 3 of this study is to determine overall adherence quantitatively as a percentage of all SNF-PCC recommendations that are implemented as well as adherence rates for specific recommendations.

3 * Describe the relevant prior experience and gaps in current knowledge. Describe any relevant preliminary data:

Palliative care is goal-directed, patient and family-centered care that focuses on a wide range of physical, psychosocial, and spiritual needs for persons with serious, life-limiting illnesses. Despite its association with improved quality of care, higher satisfaction, and better symptom management at the end of life, palliative care is not widely available to Medicare patients in the Skilled Nursing Facility (SNF) setting. We will test an evidence-based intervention derived from existing palliative care standards for adults over age 60 with life limiting illness who are admitted to a nursing home for SNF care.

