Between 14 days and 21 days after the baseline POS is administered, all subjects will be asked to complete the POSv2 again virtually via telephone. The POS will be given a total of two times to those in the INTERVENTION and CONTROL groups; at baseline and follow up (14-21 days later). During this follow-up, subjects in the INTERVENTION ARM who receive a palliative care encounter will also be asked to complete the Consultation Satisfaction Questionnaire (CSQ) survey. The CSQ measures the INTERVENTION group satisfaction and therefore will only be given to INTERVENTION group at follow up. The CONTROL group WILL NOT receive a palliative care encounter therefore a consultation satisfaction questionnaire (CSQ) is NOT appropriate to administer.

Deidentified subject demographics will be collected on all participants in the following way: Research staff will review subject's medical records and enter de-identified data into REDCap (ACTS Staff assists with research team access to subject's medical record).

The goal of the intervention is to prevent, identify and treat symptoms early in the course of SNF care, establish goal directed treatment decisions, and support the patient and family in decision making. We anticipate that many Palliative care encounters involve a single encounter with the patient and/or surrogate decision maker, but we have made allowances for follow up visits depending on individual patient and family needs (e.g., symptom management, continuing goals of care discussions). We will use usual care as the control condition. Usual care consists of traditional resources focused on skilled nursing care without services to support specialty palliative care. A usual care comparison will test whether the Palliative Care Encounter improves patient/family reported outcomes compared to traditional services. We have chosen to not use an attention control condition because the goal of this pilot clinical trial is to assess feasibility and determine the effect size of the intervention on the primary outcome.

Research staff will collect measures via phone or through a secured online template to minimize missing data at two time points (baseline & 14-21 days later) during the study. All data will be entered and managed in a Research Electronic Data Capture (REDCap) database by the RA, project manager, or the PI.

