Specific Aim 2 of the study is to estimate an effect size for the SNF-PCC intervention on patient/family caregiver reported quality of life as measured by the Palliative Outcomes Scale, whose reported estimated standard deviation is approximately 6.1.2 As such, group sample sizes of 40 each produce a two-sided 80% confidence interval for the true mean measure of effect (difference in means) with a width of 3.4 units.

2 * Provide the plan for data analysis. Include in the description the types of comparisons that are planned (e.g., comparison of means, comparison of proportions, regressions, analysis of variance, etc.), which is the primary comparison/analysis, and how the analyses proposed will relate to the primary purposes of the study:

The primary analysis will be to compare the mean pre-post changes in the Palliative Outcomes Scale (POS) between the intervention and control arms. Linear regression models will be used to compare the two groups. The within-arm changes and differences between arms will be summarized with two-sided 90% CIs and p-values corresponding to tests against the null hypothesis of no (zero) change or difference. We will also explore subgroup effects of the intervention on endpoints by testing for statistical interactions between the binary group indicator and covariates of interest such as sex, age, and race.

Other key parameters needed to plan a follow-up study will be estimated as well, including the standard deviation (SD) and intraclass correlation coefficient (ICC) of each endpoint. The ICC summarizes the degree of correlation of values among patients within a site, which is an important parameter when planning a cluster randomized controlled trial.

*ID: VIEW4E02806052800
Name: v2_Sample Size and Data Analysis*

Sharing of Results

1 * Describe whether results (study results or individual subject results, such as results of investigational diagnostic tests, genetic tests, or incidental findings) will be shared with subjects or others (e.g., the subject's primary care physicians) and if so, describe how it will be shared:
N/A

ID: VIEW4E02808CBD800
Name: v2_Sharing of Results

Psychological/Behavioral/Educational Methods & Procedures

You indicated on the "Type of Research" page that your study involves a psychological/behavioral/educational method or procedure such as a survey, questionnaire, interview, or focus group.

1 * Select all behavioral methods and procedures which apply to this study:

- Surveys/questionnaires

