Data Management and Security regarding subject data extracted from the Acts EMR as described in the Procedure section: once queried and scrubbed of identifying information manually entered into REDCap by research staff via remote access.

3 * Describe the plan to destroy the PHI collected during this study at the earliest opportunity consistent with the conduct of the research. If there is a need to retain PHI, provide a justification:
A key linking participant's identifying information to their subject ID will be destroyed upon completion of data collection.

4 * Why could the research not practically be done without access to and use of this PHI?
Waiver for recruitment: We need the PHI in order to screen participants for eligibility.

HIPAA alteration to obtain verbal authorization: We cannot do the study without their PHI after they are enrolled because we still need to follow up with the resident or LAR. We need to administer the baseline and follow up surveys at the designated timepoints and their names and numbers are needed to contact them. Their ACTs ID are needed so [name] can complete the fidelity checks and link the participant to the UMB subject ID. The research staff records the participants' names, but they will not be entered in the RedCap database. This done since we destroy names after they complete the study.

5 * Why could the research not practically be done without the waiver or alteration?

(1) Palliative care consultation is standard of care and a low risk intervention;
(2) the waiver will not adversely affect the rights and welfare of the subjects; hospice/palliative care are already being offered in this site and this trial seeks to increase the opportunity for residents and their surrogates to benefit from palliative care , while not restricting choice to forego it because it is not offered:
(3) The research cannot be practically conducted without a waiver as the trial will evaluate system-level implementation of an evidence-based intervention; requiring prospective written informed consent would introduce important selection biases greatly reducing the knowledge generated; and (4) to the extent possible, the subjects will be provided with pertinent information after participating in the trial.

These answers are also applicable to applicable for the HIPAA alteration.

6 * Will the subjects' PHI be disclosed to (or shared with) any individuals or entities outside of UM?
 Yes No

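### The primary POS comparison names no adjustment for baseline POS; adding it is a nearly free gain in precision, of a size the documents cannot fix

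*Combined protocol and SAP*

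**What the plan says.** Sample Size and Data Analysis, item 2, sets the primary analysis: "The primary analysis will be to compare the mean pre-post changes in the Palliative Outcomes Scale (POS) between the intervention and control arms". The method follows in one sentence: "Linear regression models will be used to compare the two groups". Results are to be given with two-sided 90% confidence intervals and p-values. No model equation or adjustment set is given. The only covariates named, "covariates of interest such as sex, age, and race", belong to exploratory tests of interaction with the group indicator.

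Baseline POS is available for every participant who completes the first call. Study Procedures, item 1, says: "The POS will be given a total of two times to those in the INTERVENTION and CONTROL groups", once at baseline and once 14 to 21 days later.

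On design, Justification, Objective, & Research Design, item 2, gives "Pilot clinical trial with usual care control; 40 participants in each arm". The resources section says "11 communities are involved in the study". Waiver/Alteration of Authorization, item 5, says that "the trial will evaluate system-level implementation of an evidence-based intervention". The within-site correlation is to be estimated because it is "an important parameter when planning a cluster randomized controlled trial", which refers to a later study. None of the available text says how patients or sites come to be in one arm or the other.

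**The concern.** Subtracting the baseline score fixes its coefficient at 1. Entering baseline as a covariate lets the data estimate that coefficient. Under random assignment both give an unbiased comparison, but in large samples the change-score comparison is never the more precise of the two, and it is usually less precise.

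Aim 2 is to estimate an effect size from 80 participants, and other quantities are to be estimated for planning a follow-up study. The width of the interval is therefore much of what Aim 2 delivers. The text also neither includes nor excludes baseline POS. Two analysts could both claim to follow it, one with and one without the covariate, and report different estimates and intervals.

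**Working it through.** **Inputs from the documents.** 40 per arm; two-sided 90% interval for the analysis; POS SD about 6.1 (not stated whether of a score or of a change); two POS measurements per participant.

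**Assumed, because the documents do not give them.** Patients individually randomised and independent; pre-post correlation r; ratio k of follow-up SD to baseline SD; 6.1 taken as the baseline SD.

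**The plan's own figure.** The plan states a width of 3.4 for an 80% interval on a difference in means. The formula is 2 × quantile × 6.1 × sqrt(2/40), where 6.1 × sqrt(2/40) = 1.364.

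- Normal quantile 1.2816: width 3.50.
- t quantile on 78 df, 1.2925: width 3.53.

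So 3.4 is not reproduced exactly. That is a separate small discrepancy. The percentages below are ratios of widths and depend neither on 3.4 nor on 6.1.

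**Formulas for the 90% width, n per arm.**

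- Change score: 2 × t(0.95, 2n−2) × 6.1 × sqrt(1 + k² − 2rk) × sqrt(2/n).
- Arm plus baseline: 2 × t(0.95, 2n−3) × 6.1 × k × sqrt(1 − r²) × sqrt(2/n) × sqrt(1 + 1/(2n−4)). The last factor is the expected cost of estimating the slope.

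Worked case, n = 40, k = 1, r = 0.5:

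- Change score: 2 × 1.6646 × 6.1 × 1 × 0.2236 = 4.54.
- Arm plus baseline: 2 × 1.6649 × 6.1 × 0.8660 × 0.2236 × 1.0066 = 3.96, which is 12.8% narrower.

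**Results, n = 40, equal SDs (k = 1).**

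| r | Change score | Arm + baseline | Difference |
|---|---|---|---|
| 0.3 | 5.37 | 4.36 | −18.8% |
| 0.5 | 4.54 | 3.96 | −12.8% |
| 0.7 | 3.52 | 3.26 | −7.2% |
| 0.9 | 2.03 | 1.99 | −1.9% |

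Simulation of 20,000 trials per setting gave −18.8%, −12.8% and −7.1% at r = 0.3, 0.5 and 0.7.

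**Sensitivity to the assumptions.**

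- k = 0.8: −28.7%, −23.9% and −20.2% at r = 0.3, 0.5 and 0.7.
- k = 1.25: −10.8%, −4.9% and −0.3% at the same r, and no gain for r between about 0.72 and 0.86.
- 32 per arm with both scores (20% loss, assumed), k = 1: −18.7%, −12.7% and −7.0%.
- Worst case, where the slope of follow-up on baseline is 1 (rk = 1): at 40 per arm, t(0.95,77)/t(0.95,78) × sqrt(1 + 1/76) − 1 = +0.7%. At 32 per arm the same expression with 61 and 62 df and 1/60 gives about +0.9%.
- Patient-level assignment within 11 sites, site ICC 0.05 (simulated): −18.8%, −12.9% and −7.2%.

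**How far apart the two estimates can be.** With equal SDs, a chance baseline difference of one standard error (1.364 points) separates them by (1 − r) × 1.364: 0.95, 0.68 and 0.41 points at r = 0.3, 0.5 and 0.7.

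**If sites were randomised.** Take 11 equal sites, 80/11 = 7.27 patients each, and a residual ICC of 0.05 (assumed). The design effect is 1 + 6.27 × 0.05 = 1.31, so the standard error is larger by a factor of 1.146. With about 9 df the t quantile is 1.833 instead of 1.665. The correct interval would be 1.146 × 1.833/1.665 = 1.26 times as wide as the one from a plain regression. Ignoring clustering would then matter more than the 7% to 19% gained from the covariate.

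**The case against.** The plainest reading of the plan is change regressed on arm, with covariates confined to the exploratory analyses. On that reading the ambiguity is slight, and what remains is a choice between two valid estimators. This is a pilot with feasibility as its first aim and no stated decision threshold on the POS contrast. The documents give no pre-post correlation, SD ratio or SD of change, so the size of the gain is unknown; the grid above runs from −29% to +0.7% at 40 per arm.

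Most of this stands. It limits the point to an improvement, and the percentages to illustrations. It does not remove the point: the covariate is already collected, the cost is one degree of freedom, and the possible loss is under 1%.

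The objection on design also stands. The percentages need individual randomisation, which the available text does not state. Advice that said only to adjust if assignment is random would be wrong for randomised sites unless clustering were also handled.

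A reader might infer that the unadjusted comparison is biased, or that the plan is in error. The documents do not support that: under random assignment the change-score comparison is valid. A reader might also infer from the 11 communities, the system-level wording and the planned ICC that arms are formed by site. Those statements are compatible with that design but do not establish it, and the one mention of cluster randomisation concerns a later trial. Nor can it be concluded that the assignment method was never written down, since some pages were removed before review.

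**Conclusion.** The point holds as a low-cost gain in precision and reproducibility. The primary model has no stated adjustment for baseline POS although the score is collected in both arms. Under individual randomisation, with 40 per arm, equal SDs and independent patients, adding it narrows the 90% interval by about 19%, 13% and 7% at r = 0.3, 0.5 and 0.7. Outside those assumptions the gain may be larger, smaller or nil, with a worst case of less than 1% wider. The percentages do not carry over to site-level or non-random assignment. In the non-random case the adjusted and change-score estimates can target different quantities, so the choice between them is no longer only about precision.

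**What to change.** In Sample Size and Data Analysis, item 2:

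- Make the primary estimate the arm coefficient, with its two-sided 90% interval, from a linear regression of POS change on arm and baseline POS. Using follow-up POS as the outcome gives the identical arm coefficient. Keep the raw comparison of mean changes as a supporting summary.
- State, or cross-refer to, how arms are assigned.
- If sites are randomised, use the same baseline-adjusted model with standard errors and degrees of freedom that allow for clustering by site.
- If assignment is not random, name either the adjusted or the change-score estimate as primary before the data are seen, and report the other as a sensitivity analysis.

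The cost is a few sentences in the plan and, for the covariate, one degree of freedom. No new data are needed.

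### The primary regression and its 90% CIs name no community term although a within-site ICC is planned, and the unit of assignment, which decides how much this matters, is not stated

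*Combined protocol and SAP*

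**What the plan says.** The primary analysis (Sample Size and Data Analysis, item 2) compares mean pre-post change in the Palliative Outcomes Scale (POS) between arms: "Linear regression models will be used to compare the two groups". It continues: "The within-arm changes and differences between arms will be summarized with two-sided 90% CIs and p-values". The only covariates named are sex, age and race, and those are for exploratory interactions. No site effect, random intercept or cluster-adjusted standard error is mentioned.

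The next paragraph begins "Other key parameters needed to plan a follow-up study will be estimated as well" and includes an ICC for each endpoint: "The ICC summarizes the degree of correlation of values among patients within a site". Its stated use is the planning of a later cluster randomised trial.

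The Resources section says "11 communities are involved in the study". The form's question on design (Justification, Objective, & Research Design, item 2) asks about "probability of group assignment, potential for subject to be randomized to placebo group, use of control subjects". The answer on assignment is only "Pilot clinical trial with usual care control; 40 participants in each arm". No section available for review says whether patients or communities are assigned, or that assignment is random.

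Sample Size and Data Analysis, item 1, gives a width of 3.4 units for a two-sided 80% CI with 40 per group and an SD of about 6.1. It makes no allowance for clustering.

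**The concern.** The plan expects patients in the same community to resemble each other enough for the ICC to be worth estimating, yet the analysis that it describes treats all 80 as independent. If the ICC of the change score is positive, two things can follow.

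- A within-arm mean change, read as applying beyond these communities, is known less well than its CI and p-value suggest.
- If whole communities are assigned, chance differences between communities can pass for an intervention effect, and the between-arm CI is too narrow.

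Aim 2 is to estimate an effect size, and item 2 is meant to supply parameters for a follow-up study, so stated precision is a main product of this pilot. Potential Benefits and Alternatives, item 2, looks to other nursing home residents, which makes inference beyond these 11 communities the natural reading.

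**Working it through.** **Inputs from the documents.** 11 communities; 40 patients per arm, 80 in all; SD 6.1 (not said to be the SD of a single score or of change); 80% CI width 3.4; analysis CIs at 90%.

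**Assumptions.** ICC 0.01 to 0.20, since the documents give none; communities of similar size, 80/11 = 7.27 patients each; a 5 v 6 split if communities are assigned; SD of change 6.1. Coverage does not depend on the SD, but widths do.

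**The plan's own figure.** 2 × 1.2816 × 6.1 × √(2/40) = 3.50. The half-width of 1.748 rounds to 1.7, which doubles to 3.4. The printed width is therefore the independence calculation, with no design effect.

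**Approximate coverage.** If the true variance of a mean is D times the naive one, a nominal 90% CI covers about 2Φ(1.645/√D) − 1.

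- *Within-arm, patients assigned, sites as a sample.* Each arm has 40/11 = 3.64 patients per site, so D = 1 + 2.64 × ICC = 1.13 at ICC 0.05 and 1.26 at 0.10. Coverage is 87.8% and 85.7%.
- *Communities assigned, between-arm, or within-arm with sites as a sample.* D = 1 + 6.27 × ICC = 1.31 and 1.63. Coverage is 84.9% and 80.3%.
- *Within-arm, communities assigned, target the mean of these 11.* Each arm holds about half the sites, so the between-site part is halved, not removed: D ≈ (1 − ICC) + 7.27 × ICC × ½ = 1 + 2.64 × ICC. Coverage is again about 87.8% and 85.7%.
- *Between-arm, patients balanced within site.* D ≈ 1 − ICC, so the CI is not too narrow.

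**Simulated coverage of the naive 90% CIs** (no true effect; 20,000 trials per ICC, 6,000 where marked *; Monte Carlo SE with 6,000 trials about √(0.9 × 0.1/6000) = 0.4 points):

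| Interval and target | Assignment | ICC 0.05 | ICC 0.10 |
|---|---|---|---|
| Within-arm, beyond these communities | patients | 87.1% | 84.8% |
| | communities | 84.0% | 79.6% |
| Within-arm, these 11 only | patients, simple* | 90.4% | 90.8% |
| | patients, balanced by site* | 90.8% | 92.5% |
| | communities | 87.4% | 85.7% |
| Between-arm | communities | 84.1% | 80.4% |
| | patients, simple | 89.8% | 90.0% |
| | patients, balanced by site* | 90.7% | 91.7% |

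At ICC 0.01 the shortfall is negligible: 89.5% within-arm with patients assigned; 88.5% within-arm and 88.6% between-arm with communities assigned.

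**The 80% width if communities are assigned.** Multiplying 3.50 by √(1 + 6.27 × ICC) gives 3.60, 4.01, 4.46 and 5.25 at ICC 0.01, 0.05, 0.10 and 0.20. With 11 − 2 = 9 df in place of the normal quantile, the widths are 3.89, 4.32, 4.81 and 5.67 (3.77 at ICC 0). At ICC 0.01 most of the increase comes from the 9 df and little from the correlation.

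**The case against.** The best defence is that the plan is silent on site in the model and does not exclude it. This is a short answer on an ethics form, and estimating an ICC already requires site in the dataset and a variance-component model. The between-arm comparison is primary, and under simple or site-balanced patient randomisation its CI is sound as planned. The within-arm CIs are then supporting summaries. With patients assigned, they need to be only about 1% to 12% wider at ICC 0.01 to 0.10 (√1.026 to √1.264). The larger shortfalls need community assignment, which no section states, as well as an ICC that no section gives. All of this stands, and it limits the size of the point. It does not remove it: a plan should say which model produces its primary interval, and here the reader cannot tell whether the assignment makes the simple model adequate.

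Two stronger readings are tempting.

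- *A reader might infer that communities are assigned, so that the primary CI is wrong.* The cluster-trial wording concerns a later study. Notification of all new admissions at each site (Study Procedures, item 1) and the reference to system-level implementation (Waiver/Alteration of Authorization, item 5) fit that reading but do not establish it.
- *A reader might infer that community will not be recorded, because the field list in Prospective Data, item 2, omits it.* That list is broad, staff obtain admissions from each site (Recruitment, item 1), and the ICC needs the variable. Confirmation is enough.

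The opposite assurance also fails. Patient-level assignment does not by itself make the between-arm CI safe, because randomisation is not stated and non-random assignment that is uneven by site could affect it.

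**Conclusion.** The point holds in conditional form. Within-arm 90% CIs are too narrow for inference beyond these communities if the ICC of change is positive. If communities are assigned, they are too narrow even for the mean over these 11. The between-arm CI is too narrow if communities are assigned, is sound under simple or site-balanced patient randomisation with a common effect, and is uncertain if patients are assigned non-randomly and unevenly by site. If the effect itself varies by community, the loss is small: with a site-by-arm variance of 5% to 10% of the total and site-balanced patients, simulated between-arm coverage is 89.3% to 88.6%.

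The size rests on assumed ICCs and roughly equal communities, and confidence in it is medium. What is affected is the precision that a pilot reports, not a confirmatory error rate. It should be fixed because the change is cheap and the missing assignment statement is needed in any case.

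**What to change.** 1. State the unit and method of assignment in the design section, item 2.
2. Include community in the primary model, for example a linear mixed model (REML) of POS change with arm fixed and community as random intercept. Use small-sample df, and take the between-arm CI, within-arm CIs and ICC from that one model. A fixed site effect (if patients are assigned) or a small-sample cluster-adjusted standard error is a reasonable alternative if it matches the design.
3. If communities are assigned, base the between-arm CI on about 9 df (random intercept, or site means if communities are of similar size). Restate the 80% width over a range of ICCs: about 3.9 to 5.7 at ICC 0.01 to 0.20.
4. Leave the within-arm CIs as planned only if patients are individually randomised and inference is expressly limited to these 11 communities.
5. Confirm that community is recorded.

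**Cost.** The change is analysis wording and, at most, one data field. With patients assigned, within-arm CIs widen from about 3.2 to 3.9-4.0 at ICC 0.10 and are somewhat conservative near ICC 0 (93-95% coverage); the between-arm CI is no wider. With communities assigned, within-arm CIs widen to about 4.5 at ICC 0.10. The between-arm CI at ICC 0 goes from 4.53 to 5.37 with a random intercept, which over-covers at 94.5%, or to 4.93 with site means (90.2%). With 11 sites the ICC estimate is imprecise (SD about 0.07 at ICC 0.05), so the community term should be fixed in advance and not dropped on the strength of that estimate.
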